3.1. Rationale

Dual antiplatelet therapy with aspirin and a P2Y₁₂ adenosine diphosphate (ADP) receptor inhibitor is standard therapy for prevention of thrombotic complications of percutaneous coronary intervention (PCI). The American College of Cardiology (ACC), American Heart Association (AHA), and European Society of Cardiology (ESC) practice guidelines recommend dual antiplatelet therapy with aspirin and an ADP receptor inhibitor in patients with acute coronary syndromes (ACS), particularly among those undergoing PCI (Jneid et al. 2012; Hamm et al. 2012). Landmark studies such as CURE and CLARITY-TIMI 28 established the benefit of long-term clopidogrel for up to 1 year in subjects with ACS who undergo PCI (Mehta et al. 2001; Sabatine et al. 2005). Significant variability in the response to clopidogrel has been observed secondary to genetic polymorphisms and pharmacodynamic interactions, with some individuals having minimal inhibition of ADP-induced platelet aggregation leading to the concern that some patients may be at increased risk for thrombotic events (Mega et al. 2011; Mega et al. 2010; Mega et al. 2009).

Results from the TRITON-TIMI 38 established the superior efficacy of prasugrel in combination with aspirin over clopidogrel plus aspirin in reducing ischemic events in ACS patients managed with PCI (Wiviott et al. 2007). Compared with clopidogrel, prasugrel caused higher rates of major bleeding, particularly in patients with advanced age, low body weight, previous stroke or transient ischemic attack. Since its United States (US) approval in 2009, there is insufficient observational data that directly compares outcomes between prasugrel and clopidogrel for ischemic and bleeding events. The TRANSLATE-ACS registry is a prospective observational study of approximately 12,000 patients with myocardial infarction ([MI], ST-segment elevation myocardial infarction [STEMI] or non-ST-segment elevation myocardial infarction [NSTEMI]) managed with PCI (Chin et al. 2011). The study is evaluating the effectiveness and safety of prasugrel compared with clopidogrel in the usual care environment. However, as long-term follow-up is being prospectively collected, patient informed consent is required that limits the ability to collect data on all MI patients managed with a PCI. Therefore, there are a large number of eligible patients who will not be included in the TRANSLATE-ACS database because they either did not give consent or were discharged prior to being identified and consent obtained.

A prior comparative retrospective, observational analysis between clopidogrel and prasugrel using the Premier claims database assessed the impact of treatment group on readmission rates for MI or bleeding (Bae et al. 2012). Adjusted results showed that prasugrel was associated with significantly lower acute myocardial infarction (AMI)-related rehospitalizations compared with clopidogrel 30 and 90 days post-discharge. Additionally, adjusted results showed no significant difference in bleeding-related rehospitalization rates between prasugrel- and clopidogrel-treated patients (Bae et al. 2012). However, analyses conducted in payer databases are usually less

robust than registries (for example, the ACC National Cardiovascular Data Registry [NCDR] CathPCI Registry[®]) or prospective observational studies in capturing pre-existing conditions prior to the index admission, particularly if the patients were not in the plan for the particular payer at the time of the previous diagnosis. Therefore, the true baseline profile of the cohorts may be inadequately determined (for example, missing a prior MI or stroke that may have occurred more than 12 months before the index hospitalization) resulting in inadequate adjustment of the data for unmeasured differences in known confounders. Additionally, payer databases are dependent upon claims made on discharge from the hospital, and may not differentiate from the primary event or the secondary event, especially if secondary diagnoses are allowed in the definition of an outcome event.

Hence, an observational retrospective database analysis using data collected from patients and/or their medical records at the time of index hospitalization with post-hospitalization follow-up will provide important information and will allow better adjustment for baseline differences and a more accurate representation of the results. Study B020 will utilize pooled databases from academic institutions where data is routinely collected on all patients undergoing PCI both during and after the index hospitalization. With regard to clinical and economic outcomes, this approach will provide appropriately controlled baseline characteristic collection to adjust for differences in treatment groups resulting in a robust comparison of prasugrel with clopidogrel in ACS patients treated with PCI. Additionally, this study will include many of the patients who were not able to be enrolled in TRANSLATE-ACS as their data is already captured in these institutional databases. The databases from these institutions collect a large amount of data as either part of or consistent with the ACC NCDR CathPCI Registry, which includes not only clinical characteristics but also detailed procedural characteristics of patients. Additionally, as these data are entered from patient records based on the clinical evaluation, there is no prespecified time window for capturing prior events. The centers participating in this study have also followed these patients post-hospitalization as part of the ongoing evaluation of their results. The majority of the centers have also published based on results of analyses from their individual, or in some cases combined, data (Bagai et al. 2012; Hess et al. 2012; Hess et al. 2014; Mathews et al. 2012; Wang et al. 2014).

3.2. Objectives

3.2.1. Primary Objective

To compare the composite major adverse cardiac event (MACE) outcomes (all-cause death, MI, stroke, or unplanned coronary revascularization) within 90 days of index hospital admission in patients with ACS managed with PCI (the overall ACS/PCI population) who initiated treatment in-hospital and continued at discharge with prasugrel versus those treated with clopidogrel.

3.2.2. Secondary Objectives

1. To examine the following clinical outcomes for ACS patients managed with PCI initiating treatment with prasugrel versus those treated with clopidogrel:

- a. To describe differences in the clinical and angiographic profiles of ACS patients managed with PCI treated with prasugrel versus clopidogrel
 - b. To compare the composite MACE endpoint at 30, 180, and 365 days following index hospital admission
 - c. To compare the individual components of the MACE endpoint (all-cause death, MI, stroke, and unplanned revascularization) at 30, 90, 180, and 365 days following index hospital admission
 - d. To compare prasugrel with clopidogrel with regard to the following non-fatal individual components of MACE at 90, 180, and 365 days following index hospital admission:
 1. new MI
 2. unplanned revascularization
 3. stroke
 - e. To compare all bleeding events or transfusions during index hospital
 - f. To compare bleeding-related rehospitalizations within 30, 90, 180, and 365 days from index hospital discharge with prasugrel compared with clopidogrel
 - g. To compare Academic Research Consortium (ARC) defined definite/probable stent thrombosis at 30, 90, and 365 days following index hospital admission with prasugrel versus clopidogrel
 - h. To compare composite MACE and bleeding events at 30, 90, 180, and 365 days following index hospital admission in the following pre-specified subgroups:
 1. ACS-PCI patients with no prior transient ischemic attack (TIA) or stroke
 2. ACS-PCI patients with no prior history of TIA or stroke and are:
 - a. <75 years of age, or
 - b. If ≥ 75 years of age, have diabetes mellitus or a history of MI
 3. Age ≥ 75 years
 4. Diabetes mellitus
 5. STEMI
 6. NSTEMI/unstable angina (UA)
 7. Chronic kidney disease (creatinine clearance < 60 ml/min/1.73m²)
 8. Gender
 9. Prior stroke or TIA
 10. Low body weight (< 60 kgs)
2. To compare the following economic outcomes (health resource utilization and costs) in patients treated with prasugrel versus clopidogrel for ACS patients with no prior TIA or stroke and managed with PCI (primary economic outcomes analysis population), and the overall ACS/PCI population (economic outcomes analysis subgroup):
 - a. Length of stay for index hospitalization
 - b. Readmission rates for MI, bleeding, stroke, unplanned coronary revascularization, or stent thrombosis at 30, 90, 180, and 365 days following index hospital discharge

- c. Health resource costs at 30, 90, 180, and 365 days following index hospital discharge
- d. Lost productivity due to cardiovascular death

3.2.3. Hypotheses

1. Prasugrel use will be associated with a significantly lower adjusted rate of MACE compared with clopidogrel at 90 days following index hospital admission for the index PCI among patients with ACS who undergo PCI (the overall ACS/PCI population)
2. Prasugrel use will be associated with a significantly lower adjusted rate of health resource utilization compared with clopidogrel at 30 days from index hospital discharge among all patients with ACS who undergo PCI and those without a prior TIA or stroke.

[figure not shown]
3.3. Research Design

3.3.1. Study Design

Study B020 is designed as a retrospective cohort study evaluating data for patients presenting with ACS managed with a PCI from 6 to 12 academic centers in the US from 01 January 2010 to 30 June 2013, with any follow-up data available for analysis. This study will evaluate the comparative effectiveness and economics of prasugrel relative to clopidogrel in approximately 8,600 patients (minimum 4,300 receiving prasugrel) in a usual care environment from academic centers in the US. These academic centers maintain institutional databases related to baseline characteristics, procedural characteristics and clinical and economic outcomes during and following index hospitalization of patients with ACS undergoing PCI.

The participating academic centers will run a query in their ACS-PCI database to identify all patients who received prasugrel or clopidogrel between 01 January 2010 and 30 June 2013. The study period was selected based on the approval and steady availability of prasugrel in the US market at the end of 2009 and by the need for a study with a minimum 90-day follow-up in this population. The primary endpoint of the study will be at 90 days from index hospital admission; at this point in therapy, the adherence rate is expected to continue to be high while the switching rate is expected to be low ($\leq 10\%$).

Figure 1 illustrates the study time periods.

Abbreviations: ACS = acute coronary syndromes; PCI = percutaneous coronary intervention.

Figure 1. Study B020 design for patients with ACS managed with PCI and treated with prasugrel or clopidogrel between 01 January 2010 and 30 June 2013.

3.3.2. Data Source

Each of the academic centers selected to participate in Study B020 provided information on the patterns of antiplatelet use for ACS patients undergoing PCI and specifically their volumes for the period from 01 January 2010 to 30 June 2013 through a site selection questionnaire. Each of the participating centers maintains high quality institutional databases of both in-hospital and post-discharge follow-up events. The data in these sets are derived primarily from the NCDR CathPCI database while the post-discharge follow-up data is simple physician-determined diagnoses at time of hospitalization. The index hospital data is collected at most sites according to the definitions used in CathPCI. No adjudication of the data will be performed. These databases do not typically include prescriptions, adherence, or outpatient encounters. This project will extract data from the participating ARC data sets using standardized extraction sheets with standardized definitions. Extracted data will be entered in a Core Study Dataset for data analyses.

3.3.3. Study Populations

Inclusion criteria: Adult patients:

1. At least 18 years of age
2. Diagnosed with ACS (STEMI, NSTEMI, UA) and managed by PCI during index hospitalization between 01 January 2010 and 30 June 2013
3. Initiated use of prasugrel or clopidogrel during index hospitalization either prior to, during, or in the peri-procedural period (as defined below) of the index PCI and were discharged on the same medication as initiated during the peri-procedural period. Patients initiated on 1 agent prior to PCI and then switched to the other agent in the peri-procedural period (prior to, during, or ≤ 3 hours post-procedure) will also be eligible for analysis.

Subgroups of interest:

1. ACS-PCI patients with no prior TIA or stroke
2. ACS-PCI patients with no prior history of TIA or stroke and are:
 - a. <75 years of age, or
 - b. If ≥ 75 years of age, have diabetes mellitus or a prior history of MI
3. Age ≥ 75 years
4. Diabetes mellitus

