3.4. Plan of Analysis

3.4.1. Methods

Analyses comparing outcomes of interest between prasugrel and clopidogrel groups will be conducted unadjusted and adjusted (using inverse probability weight [IPW] method) for demographic, clinical, and procedural differences as described below. The primary comparison will be between patients treated with prasugrel versus clopidogrel in an intention-to-treat (ITT) fashion, after adjustment for demographic, clinical, and procedural differences as described below. The primary endpoint of interest is the first occurrence of MACE within 90 days from hospital admission for the index PCI. For the primary outcome of interest, the crude unadjusted 90-day rates of MACE will be calculated for each group using the Kaplan-Meier method, also including index hospital events. Crude rates will be compared between groups using the log-rank test (Kalbfleisch et al. 1980; Prentice et al. 1978).

For descriptive purposes, baseline clinical (including laboratory evaluations) and demographic and procedural characteristics will be compared between groups using student's t-test and chi-square test for continuous and categorical variables, respectively.

In-hospital (that is, post-procedural) outcomes will be assessed by comparing the proportion of post-procedural events between prasugrel and clopidogrel groups. These binary proportion comparisons will be performed using a Chi-square test between groups.

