Total follow-up for each patient in Study B020 will be defined as time until death, last follow-up or 365 days following hospital admission for the index PCI, whichever comes first. To evaluate the associations between treatment group (prasugrel versus clopidogrel) and dependent outcomes, hazard ratios will be calculated using Cox proportional hazards regression. Median event free survival time will also be reported. In addition to age, gender and race, any baseline demographic, clinical, or procedural characteristic demonstrating a significant ($p < 0.1$) difference between groups will be included in the multivariable model. The model will also include other covariates that might be pertinent to the clinical outcome even if there are no significant differences in this cohort (for example, diabetes mellitus [DM], smoking status, etc.). Using these candidate covariates, a final multivariate model will be generated using a stepwise selection procedure to ensure model parsimony. The primary exposure of interest (prasugrel versus clopidogrel) will be forced in this final model.

As a separate sensitivity analysis, IPW will be used to adjust the selection bias for the treatment allocation. The propensity score will be generated using a non-parsimonious logistic regression model with the dependent variable as prasugrel versus clopidogrel treatment. From this model, each patient will be ascribed a predicted probability that reflects the propensity to have received prasugrel or clopidogrel at discharge. Inverse probability weights will be derived for all observations using the propensity scores, and then regression analyses will be repeated using these weights.

The primary analysis will include the overall ACS/PCI population. All analyses will be repeated in the all subgroups listed in Section 3.3.3.

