5.3 Study Populations

Inclusion criteria:

1. At least 18 years of age at time of index PCI.
2. Diagnosed with ACS (STEMI, NSTEMI, UA) and managed by PCI with stent implantation during the index hospitalization between 01 January 2010 and 30 June 2013
3. Treatment with prasugrel or clopidogrel during index hospitalization either prior to, or during the peri-procedural period (as defined below)

Populations of Interest:

1. All ACS-PCI patients
2. ACS-PCI patients with no prior TIA or stroke
3. ACS-PCI patients with no prior history of TIA or stroke and are:
 - i. <75 years of age, or
 - ii. ≥ 75 years of age with diabetes mellitus or a prior history of MI
2. Diabetes mellitus

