6.1 Methods

Primary Objective

The exposure groups for the primary analysis will be defined as those patients receiving prasugrel or clopidogrel at the time of PCI (i.e. loaded peri-procedurally or currently taking in the absence of a load). All patients will be assigned to one of these mutually exclusive groups irrespective of medication administered at discharge. Patients administered both medications at the time of PCI will be excluded for any comparative analyses of treatments.

For descriptive purposes, baseline clinical (including laboratory evaluations) and demographic and procedural characteristics will be compared between groups using student's t-test and chi-square test or Fisher's exact test for continuous and categorical variables, respectively.

In-hospital (that is, post-procedural) outcomes will be assessed by comparing the proportion of post-procedural events between prasugrel and clopidogrel groups. These crude unadjusted binary proportions will be performed using a Chi-square test between groups.

The primary endpoint of interest is the first occurrence of MACE within 90 days from date of index PCI. For purposes of this primary analysis, event-free patients will be censored at 90 days or last contact, whichever comes first. For the primary outcome of interest, the crude unadjusted 90-day rates of MACE will be calculated for each group using the *Kaplan-Meier method, also including index hospital events*. Crude rates will be compared between groups using the logrank test (Kalbfleisch et al. 1980; Prentice et al. 1978).

To evaluate the adjusted associations between treatment group (therapy initiation with prasugrel versus clopidogrel) and the primary MACE outcome, hazard ratios will be calculated using Cox proportional hazards regression that are stratified by the propensity to receive either prasugrel or clopidogrel.

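### The protocol restricts its primary cohort to patients discharged on the drug used around PCI, yet counts death from admission; the SAP's primary cohort has no discharge condition, and the two must be reconciled.

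*Protocol*

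**What the plan says.** **Protocol.** The primary objective (3.2.1) concerns patients "who initiated treatment in-hospital and continued at discharge with prasugrel versus those treated with clopidogrel". Criterion 3 of 3.3.3 makes this an entry condition: patients must have started prasugrel or clopidogrel around the index PCI and "were discharged on the same medication as initiated during the peri-procedural period". Its last sentence also admits patients switched between agents up to 3 hours after the procedure. The propensity score in 3.4.1 models the "propensity to have received prasugrel or clopidogrel at discharge".

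On the outcome, 3.4.1 states: "The primary endpoint of interest is the first occurrence of MACE within 90 days from hospital admission for the index PCI". MACE includes all-cause death. Crude 90-day rates are calculated "using the Kaplan-Meier method, also including index hospital events", and the primary comparison is described as intention-to-treat.

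**SAP.** Criterion 3 of Section 5.3 reads "Treatment with prasugrel or clopidogrel during index hospitalization either prior to, or during the peri-procedural period (as defined below"), with no discharge condition. Section 6.1 forms the exposure groups from the drug received at PCI: "All patients will be assigned to one of these mutually exclusive groups irrespective of medication administered at discharge". Its time origin also differs: "The primary endpoint of interest is the first occurrence of MACE within 90 days from date of index PCI". The cohort on the same drug at PCI and at discharge appears in 6.1 as sensitivity analysis 5, which is limited to out-of-hospital MACE and leaves out in-hospital deaths.

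**The concern.** A patient who dies during the index stay is never discharged on any drug and so cannot satisfy protocol criterion 3. A survivor whose drug is changed later than 3 hours after PCI, for example following an in-hospital thrombotic or bleeding event, also fails it. Entry therefore depends on what happens after treatment starts, while the endpoint clock is already running. Under the protocol the in-hospital death component of MACE is zero by construction, although the text says index-hospital events are counted.

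This affects the primary comparison. Selecting on survival and drug persistence to discharge removes early failures from both arms, in proportions nobody can state in advance. The resulting hazard ratio describes patients who left hospital on their starting drug, not everyone who started it. Two analysts working in good faith, one from each document, would analyse different primary populations.

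**Working it through.** **1. The rules side by side**

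| | Protocol | SAP |
|---|---|---|
| Entry | Discharged on the peri-procedural drug (3.2.1, 3.3.3) | Treated before or during the peri-procedural period (5.3) |
| Exposure | Drug at discharge in the propensity model (3.4.1) | Drug at PCI (6.1) |
| Time origin | Index admission (3.4.1) | Index PCI (6.1) |
| In-hospital deaths | Cannot enter | Enter and count |
| Both drugs around PCI | Switchers within the window eligible (3.3.3) | Given both at PCI: excluded from comparisons (6.1) |
| Non-fatal in-hospital events, same drug at discharge | Count | Count |

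The SAP also adds stent implantation to criterion 2.

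**2. Inputs for size**

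- From protocol 3.4.8 and SAP 6.8: control 90-day MACE 8.0%, 20% relative reduction (6.4% on prasugrel, read as a risk ratio), 4,303 per arm.
- Assumed, because neither document gives a figure: in-hospital death of 1% or 2% on clopidogrel.
- Assumed: the 8.0% includes in-hospital deaths.
- Two-sided alpha of 0.05; the documents do not state sidedness.

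Planned events: 4,303 × 0.080 + 4,303 × 0.064 = 344 + 275 = about 620.

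On the stated 4,303: a two-sided comparison of 8.0% with 6.4% needs 4,096 per arm, and 4,096/0.9 = 4,552, so 4,303 is not reproduced with full 10% inflation. That is a separate matter; 4,303 is used here as given.

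**3. Effect on the ratio**

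With in-hospital death proportions d_c and d_p, the risks among patients discharged alive are (0.080 − d_c)/(1 − d_c) and (0.064 − d_p)/(1 − d_p).

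| d_p / d_c | d_c = 1% | d_c = 2% |
|---|---|---|
| 0.5 | 5.93% / 7.07% = 0.84 | 5.45% / 6.12% = 0.89 |
| 0.8 | 5.65% / 7.07% = 0.80 | 4.88% / 6.12% = 0.80 |
| 1.0 | 5.45% / 7.07% = 0.77 | 4.49% / 6.12% = 0.73 |
| 1.25 | 5.22% / 7.07% = 0.74 | 4.00% / 6.12% = 0.65 |

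The shift can go either way, and it vanishes when in-hospital deaths follow the planned ratio.

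**4. Effect on power, ratio held at 0.80**

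Power = Φ{[|p_c − p_p|√n − 1.96√(2p̄(1 − p̄))] / √(p_c(1 − p_c) + p_p(1 − p_p))}, with n = 4,303 per arm and no dropout.

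| Deaths removed | p_c | p_p | Events in 8,606 | Power |
|---|---|---|---|---|
| None | 8.00% | 6.40% | 620 | 81.9% |
| 1% | 7.07% | 5.66% | 548 | 76.7% |
| 2% | 6.12% | 4.90% | 474 | 70.2% |

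These power figures belong with the no-shift case only. Where the exclusion itself moves the ratio, power moves with it: with equal deaths in both arms the absolute difference is kept and power does not fall.

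These tables cover deaths only. Survivors excluded for a later switch cannot be sized from the documents.

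**The case against.** The strongest reply is that the SAP has already dealt with this. It reads as the later text: it describes the prospective registry in the past tense and names eight centres where the protocol allows six to twelve. Its primary analysis does not condition on discharge drug, and it pairs the discharge-defined cohort only with out-of-hospital events. A reader might infer that the planned primary hazard ratio is biased or uninterpretable. The documents do not support that for the SAP analysis; the defect lies in the protocol text and in the mismatch. What survives is that no passage says the SAP replaces the protocol population. The SAP also refers to a definition of the peri-procedural period that it never gives; the only stated window sits inside the protocol criterion at issue. Discharge grouping also lingers in SAP Section 12, where Table 2 is listed by therapy at PCI but its mock-up is titled by discharge therapy.

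A reader might also infer that in-hospital deaths will be lost at extraction, or that centres will differ in whether they supply them. Both documents describe a query for all patients who received either drug, with discharge drugs as separate fields, and sensitivity analysis 5 presupposes that in-hospital deaths are in the dataset. Loss is a possibility if a centre applies protocol criterion 3, not something the documents show.

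Finally, the size depends on the 8.0% including in-hospital deaths. The plan attributes that rate to two earlier studies, one of which it describes as examining readmissions and the other as limited by consent. If the rate largely excludes such deaths, these figures do not apply.

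**Conclusion.** Wrong as written in the protocol. Sections 3.2.1, 3.3.3 and 3.4.1 combine a cohort selected at discharge with an endpoint that counts death from admission under an ITT label, and SAP 5.3 and 6.1 set a different primary population. An analysis following the protocol rule would not be an ITT estimate.

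The contradiction rests on the text alone. Its numerical size is illustrative and depends on the two assumptions about in-hospital death and the 8.0% rate: a shift from 0.80 to anywhere between 0.73 and 0.89 across equal, proportionate and halved in-hospital deaths, including no shift at all. If the ratio holds at 0.80, the cost is lost events and 5 to 12 points of power.

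It would go too far to say that all in-hospital events are lost. Non-fatal in-hospital MI, stroke and unplanned revascularization still count in patients discharged on the same drug; only in-hospital deaths and patients switched after the window drop out.

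**What to change.** Amend protocol 3.2.1, criterion 3 of 3.3.3 and the propensity exposure in 3.4.1 to the SAP's primary population: drug at PCI, regardless of discharge drug or survival to discharge.

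In the same edit, reconcile across both documents:

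- the time origin (admission or index PCI), since exposure fixed at PCI with time counted from admission leaves person-time before exposure;
- the peri-procedural window, which the SAP invokes without defining;
- the handling of patients given both drugs around PCI;
- the SAP's added stent requirement, so that the entry criteria match.

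State in the site extraction instructions that in-hospital deaths and in-hospital switchers are to be extracted. Keep the discharge-defined cohort for SAP sensitivity analysis 5 and for the economic tables by discharge therapy, not for the primary clinical analysis. Correct the title of the Table 2 mock-up.

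The cost is protocol wording, matching definitions in the SAP and one instruction line. Admission, PCI, discharge and death dates, loading drug and discharge drug are already in Attachment 1, so no new data field is needed.
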